20,000 men and women, aged ≥ 60 and ≥ 65 , respectively. VITAL cohort assembly has begun and baseline mailings will begin in January 2010. The three outcomes that we will test in this ancillary grant include: prevention of autoimmune diseases, and effects on systemic inflammation and chronic knee pain. At the end of a 3 month run-in period, participants will be randomly assigned to one of four treatment groups for 5 years: vitamin D₃ (2000 IU/d) and fish oil (EPA+DHA, 800 mg/d); vitamin D₃ and fish oil placebo; placebo vitamin D₃ and fish oil; and placebo vitamin D₃ and placebo fish oil. At 1-year intervals, participants will receive a new supply of pills, and assessments of incident autoimmune diseases, compliance and potential side effects. All autoimmune disease endpoints will be confirmed by medical record review by the physician endpoints committee. We anticipate validation of 600 incident cases of autoimmune disease, giving us sufficient statistical power to assess supplement effects on disease incidence. Blood samples at baseline and after 1-2 years follow-up will be collected in a subcohort of 2000 individuals and analyzed for changes in biomarkers of systemic inflammation: C-reactive protein, interleukin-6, and tumor necrosis factor- α . Approximately 2000 individuals with chronic, daily knee pain on baseline screening will be followed with annual questionnaires, providing ample statistical power to evaluate the effects of vitamin D and fish oil upon changes in chronic knee pain. This trial will be very cost-effective as it will be conducted by mail. Each participant will be randomly assigned in a 2x2 factorial design to vitamin D, fish oil, both agents, or both placebos (anticipated mean treatment duration of 5 years).

Study population. The study population will be that of the parent VITAL trial, described in Partners' IRB approved protocol 2009-P-00127; clinicaltrials.gov NUMBER01169259. It will include approximately 20,000 apparently healthy participants—10,000 men aged ≥ 60 and 10,000 women aged ≥ 65 , ages at which rates of chronic diseases, including autoimmune diseases and knee OA pain, increase substantially.

Cohort assembly, eligibility, run-in and randomization are described in Partners' IRB approved protocol 2009-P-00127; clinicaltrials.gov number 01169259.

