When specimens or data collected by research collaborators outside Partners will be sent to Partners investigators, indicate from where the specimens/data will be obtained and whether the specimens/data will contain identifiers that could be used by Partners investigators to link the specimens/data to individual subjects. When appropriate, submit documentation of IRB approval and a copy of the IRB-approved consent form from the institution where the specimens/data were collected.

Not applicable.

Protocol Biostatistical Analyses

Separate analyses will be conducted for the 3 endpoints and for the 2 nutritional supplements, vitamin D and omega-3 fatty acids. Analyses of treatment effects will be based on the intent-to-treat principle. The first analysis will compare baseline characteristics by randomized treatment

assignment to ensure that balance was achieved by the randomization. Characteristics to be examined include known risk factors for autoimmune diseases, systemic inflammation, and chronic knee pain including: age; gender; race/ethnicity; family history of autoimmune disease; BMI; smoking; alcohol use; physical activity; co-morbid medical conditions such as hypertension, hyperlipidemia, diabetes, and cardiovascular disease; and baseline vitamin D and omega-3 fatty acid levels as assessed by dietary questionnaire in all participants and blood assays in the case-cohort subsample. The large sample size, as well as successful balance of known potential confounders, will provide assurance that unmeasured or unknown potential confounders will also be equally distributed across randomized treatment groups. For autoimmune disease, we will estimate the intervention effects on the primary endpoint of total incident autoimmune disease. For inflammatory biomarkers, we will assess changes in linear biomarkers (log transformed if necessary). For chronic knee pain, the primary endpoint will be assessed by the WOMAC pain scale; secondary analyses will test for decreases in WOMAC stiffness, function and global scales, as well as analgesic use separately. Data analyses will be performed using SAS 9.2 (SAS Institute Inc., Cary, North Carolina).

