Inflammatory Biomarkers. In a randomly selected subcohort of 2000 participants, blood will be collected at both baseline and follow-up and changes in levels of plasma biomarkers of inflammation will be investigated. As inflammatory biomarkers are associated with age, BMI, medication use and cigarette smoking, we will again ensure that baseline characteristics are balanced in the four treatment groups in this subcohort and will additionally adjust for them in our analyses. Inflammatory Biomarkers (hsCRP, IL-6, TNFR2) will be analyzed as continuous outcomes. Descriptive statistics such as the minimum, maximum, range, median, and mean are used to summarize the variable as well as detect outliers and missing values. Exploratory graphical techniques such as Boxplots, Histograms, Quantile-Quantile plots, and Stem and Leaf plots will be used to further examine the distribution of each biomarker. Natural log transformation may be necessary based on our past analyses¹⁰⁵. Unadjusted treatment effects will be evaluated using two-way Analysis of Variance (ANOVA) or Kruskal–Wallis nonparametric test. Multiple linear regression will be used to test the association between the biomarkers (or transformed scale) and treatment groups, while adjusting for age and gender. Model assumptions and goodness of fit will be evaluated using applicable techniques³⁸⁷. In a secondary analysis, additional adjustment for the other potential predictors including baseline biomarkers will be performed.

Chronic Knee Pain. In a separate subcohort of approximately 2000 individuals with baseline chronic daily knee pain and no history of total knee replacement surgery, we will evaluate changes in level of knee pain over the course of the RCT. The annual measure of WOMAC knee pain subscale will be the primary outcome. Angst and colleagues examined data from 122 prospectively-followed individuals with knee OA in a comprehensive rehabilitation program to define the minimally clinically important difference (MCID) in WOMAC scores (range 0-10), for

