b. Inflammatory biomarkers. Our power calculations are based on past changes in systemic inflammatory biomarkers in large cohort analyses and we have first assumed that only one agent is effective, that compliance is 80% and that the cohort of 2000 followed over two years for changes in biomarkers is randomly drawn from each of the four treatment groups. (**Table 5**) Based on the distribution of hsCRP, IL-6 and TNFR2, natural log-transformation may be used for power analysis if applicable. According to NHANES 1999-2002

Observed reduction %	hsCRP	IL-6	TNFR2
20	0.72	0.55	>0.99
25	0.89	0.74	>0.99
30	0.97	0.88	>0.99
40	0.99	0.99	>0.99

†Assuming compliance to be 80%.

data, median hsCRP level is 2.8 mg/L for men aged ≥60 and women aged ≥65³⁹¹. Using a two-sided type I error of 0.05, the sample size of 500 patients with compliance of 80% in each group will achieve 89% power to detect a 25% reduction of hsCRP using a two-sided t test (based on log-transformed scale). Pai and

colleagues examined plasma levels of TNFR2 and IL-6 as biomarkers for cardiovascular disease risk among participants in the Nurses' Health Study and the Health Professional Follow-up Study (mean age 60.3 for women, 65.2 for men)¹³⁵. The mean TNFR2 was 2370 pg/ml (SD 795 pg/ml) and the median IL-6 level was 1.6 pg/mL. A sample size of 500 per group with compliance of 80% will achieve more than 99% power to detect 20%-40% reduction of TNFR2 with a two-sided significance level of 0.05. Based on a log-transformed scale, we will have 88% power to detect a 30% reduction in IL-6.

c. Chronic knee pain. In the study by Angst and colleagues, the mean global score was 4.8 and the MCID for improvement in pain was 0.75, for stiffness 0.72, for function 0.67 and for global

	Baseline Score	SD	MCID	Power
WOMAC knee pain	4.83	2.25	0.75	0.99
WOMAC knee stiffness	4.61	2.67	0.72	0.96
WOMAC knee function	4.81	2.18	0.67	0.99
WOMAC Global	4.80	2.09	0.67	0.99

SD= standard deviation per Angst, 2002 MCID= minimally clinically important difference

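### The main biomarker regression leaves out each marker's own baseline value, although it is measured in the same 2,000 people; moving it into the main model gives a modest gain in precision at no cost.

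*Combined protocol and SAP*

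**What the plan says.** The Research Design and Methods section plans blood samples at baseline and after one to two years in a subcohort of 2,000, to be "analyzed for changes in biomarkers of systemic inflammation". The opening of Protocol Biostatistical Analyses also points to change: "For inflammatory biomarkers, we will assess changes in linear biomarkers (log transformed if necessary". Section b of Power calculations describes "the cohort of 2000 followed over two years for changes in biomarkers is randomly drawn from each of the four treatment groups".

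The Inflammatory Biomarkers paragraph gives the methods in order:

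- After listing age, BMI, medication use and smoking as correlates of the markers, it says the authors will check balance on them and "will additionally adjust for them in our analyses".
- Unadjusted effects are assessed by two-way ANOVA or Kruskal-Wallis.
- Multiple linear regression is then used to "test the association between the biomarkers (or transformed scale) and treatment groups, while adjusting for age and gender".
- The baseline value of the marker appears last: "In a secondary analysis, additional adjustment for the other potential predictors including baseline biomarkers will be performed".

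The regression sentence does not say whether its dependent variable is the follow-up level or the change.

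**The concern.** In a two-sample design the outcome's own baseline value is usually among its strongest predictors. Here it is collected in everyone in the subcohort, yet the main regression does not use it as a covariate. A change score does use it, but by subtraction, which fixes its coefficient at 1. A regression on baseline estimates that coefficient and, in large samples, is never less precise.

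No bias is at stake, since assignment is randomised. What is at stake is that the main Aim 2 estimates for vitamin D and fish oil would carry wider intervals than necessary, while the more precise estimate is reported as secondary. If the two differ in significance, promoting the better one after unblinding would be post hoc.

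**Working it through.** **Inputs from the documents.** Subcohort 2,000 in a 2x2 design; two-sided 0.05; 500 per group in section b of Power calculations. Table 5 powers: hsCRP 0.72 and 0.89 at 20% and 25% reductions; IL-6 0.55, 0.74 and 0.88 at 20%, 25% and 30%; TNFR2 above 0.99 throughout. "The mean TNFR2 was 2370 pg/ml (SD 795 pg/ml) and the median IL-6 level was 1.6 pg/mL".

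**Assumed, because not given.** The baseline to follow-up correlation r (0.4 to 0.8), the ratio k of follow-up SD to baseline SD (1, then 0.8 and 1.2), and the log-scale SDs of hsCRP and IL-6.

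**1. The plan's own figure.** For TNFR2 at 20%, the shift is 0.20 x 2370 = 474. Then 474 / (795 x sqrt(2/500)) = 9.43, and power is above 0.9999. The stated value reproduces. The hsCRP and IL-6 powers cannot be derived independently. With an SD back-solved from the 25% row, each set of rows fits within two points if the shift is the stated percentage of the log median (implied SD about 1.28 for hsCRP and 0.71 for IL-6).

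**2. Variance, equal SDs.** In units of the single-measurement variance, the comparison has variance proportional to 1 for the follow-up level, 2(1 - r) for the change, and 1 - r² with baseline as a covariate. Hence adjusted/change = (1 + r)/2 and adjusted/level = 1 - r².

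| r | adjusted/change | interval width ratio | adjusted/level |
|---|---|---|---|
| 0.4 | 0.70 | 0.837 | 0.84 |
| 0.6 | 0.80 | 0.894 | 0.64 |
| 0.8 | 0.90 | 0.949 | 0.36 |

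The gain over a follow-up-level analysis exceeds the gain over change only when r is above 0.5. Simulation of the 2x2 design with 2,000 people agrees: the standard error ratio against change was 0.868 at r = 0.5 and 0.929 at r = 0.7 (formula 0.866 and 0.922).

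**3. Variance, unequal SDs.** Adjusted/change = k²(1 - r²) / (1 + k² - 2rk). At r = 0.4, 0.6, 0.8:

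- k = 1.2: 0.817, 0.922, 0.997
- k = 0.8: 0.538, 0.602, 0.640

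The saving therefore runs from 0.3% to 46% across these scenarios.

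**4. Power for each agent.** The plan says: "Separate analyses will be conducted for the 3 endpoints and for the 2 nutritional supplements, vitamin D and omega-3 fatty acids". With no interaction, each main effect compares about 1,000 with 1,000, so the non-centrality is sqrt(2) x (1.960 + z of the Table 5 power). For IL-6 at 20% this is 1.414 x (1.960 + 0.126) = 2.950, power 0.839. For hsCRP at 20% it is 3.596 (0.949), and for IL-6 at 25% it is 3.682 (0.957).

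If Table 5 describes a change-score analysis, divide by sqrt((1 + r)/2):

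| Effect | unadjusted change | adjusted, r = 0.4 | r = 0.6 | r = 0.8 |
|---|---|---|---|---|
| IL-6 20% | 0.839 | 0.941 | 0.910 | 0.875 |
| hsCRP 20% | 0.949 | 0.990 | 0.980 | 0.966 |
| IL-6 25% | 0.957 | 0.993 | 0.984 | 0.973 |

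Table 5 may instead rest on the SD of a level, since the one SD given (TNFR2) is of that kind. The change score then divides by sqrt(2(1 - r)) and the adjusted model by sqrt(1 - r²). IL-6 at 20% goes from 0.768 to 0.896 at r = 0.4, from 0.910 to 0.958 at r = 0.6, and is above 0.99 either way at r = 0.8.

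**The case against.** The best counter-argument is that this is a refinement and not a defect. The planned estimate is unbiased, a change score already draws on baseline, the adjusted model is planned, and the section on resampling from the trial promises control of any imbalance that is seen. All of that is true. But controlling observed imbalance does not make baseline a fixed term, and the precision gain arises even when the groups are perfectly balanced. Nor does the sentence on age, BMI, medication use and smoking fill the gap, because the baseline marker is not in its list.

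Second, power hardly moves. On the same 1,000 v 1,000 change-score basis, the two log-scale effects that the power text singles out already have power of about 0.995 (hsCRP, 25%) and 0.993 (IL-6, 30%). Only three cells of Table 5 start below 0.99, and all three exceed 0.80. This stands: on that basis the benefit is mainly narrower intervals.

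Third, the plan does not label any biomarker model primary. That is so, but calling the baseline-adjusted analysis secondary places it behind the others.

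Fourth, the IL-6 assay sensitivity (0.94 pg/mL) is not far below the quoted median of 1.6, so some values may be floored. Under assumed log SDs, setting low values to the limit shrinks a true 20% reduction by about 25% to 40% under both methods, while the relative variance gain survives (ratios about 0.61 to 0.87). Flooring is thus a separate matter that does not favour the change score.

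**Conclusion.** The concern holds. The main biomarker regression omits the baseline value of its own outcome, and the Aim 2 estimates are less precise than they could be.

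With change as the outcome, equal variances and r between 0.4 and 0.8, variance would be 30% to 10% lower and intervals 16% to 5% narrower. The gain almost vanishes if follow-up SD is 20% above baseline and r = 0.8; it is larger if follow-up SD is below baseline, or if the outcome is the follow-up level and r exceeds 0.5. The direction does not change in any scenario examined. Power improves noticeably only for IL-6 at a 20% reduction. All sizes rest on assumed correlations and SDs. This is a matter of efficiency, worth changing because it is free, and not a threat to validity.

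**What to change.** Name one main Aim 2 model for each marker: follow-up value regressed on vitamin D assignment, fish oil assignment, baseline value of the same marker on the same scale (log where the planned distribution check calls for it), age and sex. Once baseline is in the model, taking change or follow-up value as the outcome gives the same treatment estimate, so the stated aim of assessing change is kept and the ambiguity about the dependent variable disappears. Keep the unadjusted analysis and the model with age and gender only as supportive.

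The cost is a change of SAP wording and one degree of freedom out of about 2,000. No new samples, assays or participants are needed, because both blood draws and the adjusted model are already in the plan.

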Autoimmune Disease Incidence. In this 2x2 factorial design, the primary aim is to compare the main effects of intention-to-treat with vitamin D and with fish oil upon autoimmune disease incidence. Initially, we will compare Kaplan-Meier curves to graphically display the survival functions across different treatment groups and a log-rank test to test the difference. We will use Cox proportional hazards models to assess the main and interaction effects of the treatment groups. The unadjusted risk ratios and their 95% CIs will be used to measure the strength of risk across different treatment groups. The proportional hazard assumption will be tested based on the smoothed plots of the scaled Schoenfeld residuals³⁸⁶. To estimate the cumulative incidence function, a nonparametric estimate will be obtained using the Kaplan–Meier method. Given randomization and blinding of 20,000 individuals in this RCT, most important covariates will be equally distributed. But, in secondary analyses, we will assess the effects of controlling for age, sex and other possible strong predictors, such as family history of autoimmune disease; baseline levels of inflammatory biomarkers, vitamin D, EPA and DHA; dietary vitamin D, EPA and DHA intake; BMI and physical activity.

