power, the following assumptions were made: (1) a 2x2 factorial trial in 10,000 men aged ≥ 60 and 10,000 women aged ≥ 65 ; (2) independent and equal allocation of participants to each treatment in the trial (for Aim 1); (3) an age distribution based on that observed at baseline in our past RCTs for men aged ≥ 60 and women aged ≥ 65 ; (4) trial follow-up of 5 years, with little loss to follow-up as achieved in our past RCTs; and (5) compliance of 80% similar to that in published trials upon which our estimated rate ratio (RR) reductions are based. Power calculations were performed using the observed RR, given past observed effects and assuming

a compliance of 80%. The corresponding true relative risk (RR) with perfect compliance is also calculated.

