a. Incident autoimmune diseases. As in **table 1**, we estimate the annual incidence of total autoimmune diseases in a U.S. population over age 60 to be approximately 1000 cases per 100,000 individuals per year: thus, in this trial of 20,000 individuals for 5 years, 1000 incident cases. (**Table 2**) Conservatively, we will validate 60% of these 1000 cases, or 600 cases, with 150 occurring in the placebo group and fewer in the intervention groups if they are effective. Given the clustering of autoimmune diseases within individuals, some incident cases will occur within the same individuals, and these will be analyzed as discrete endpoints. Power is given for a a logrank test³⁹⁰ based on the proportional hazard rates with a significance level of 0.05. (**Table 4**) Assuming that only one agent is effective, with 5 years of treatment and follow-up, we will have 81% power to detect an observed RR of 0.70 (or 30% risk reduction) for the primary endpoint of autoimmune disease incidence. For the secondary endpoint of AITD, we will have 85% power to detect a 40% risk reduction. If both agents are effective in preventing autoimmune disease but act independently, power would be reduced slightly due to a somewhat smaller overall number of events. If the agents interact, however, power will be affected to the extent of the interaction. Should the agents act synergistically, power would increase. For example, if the effect of each agent alone is a reduction of 15%, but in combination the effect is stronger, with an additional 10% decrease, the RR comparing the combined group to the all placebo group would be 0.65, versus 0.72 with additive effects (on the multiplicative scale). Power for the total effects would increase to 91%. Power is shown for a given observed reduction in risk, assuming 80% compliance similar to that seen in trials such as WHS and PHS.

Observed RR†	True RR	Autoimmune Disease	AITD
0.70	0.67	0.81	0.62
0.65	0.61	0.91	0.75
0.60	0.56	0.97	0.85

†Observed RR=intent-to-treat RR assuming compliance 80%. True RR= with perfect compliance. AITD= autoimmune thyroid disease

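### Table 4's power for total autoimmune disease fits one factorial cell against another, not the main effects named as the primary aim, and its True RR column does not follow from 80% compliance

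*Combined protocol and SAP*

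**What the plan says.** **Primary comparison.** Under Autoimmune Disease Incidence in the Protocol Biostatistical Analyses, "the primary aim is to compare the main effects of intention-to-treat with vitamin D and with fish oil upon autoimmune disease incidence". The same paragraph also plans Kaplan-Meier curves and a log-rank test across the treatment groups.

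**Power assumptions.** The opening of Power calculations sets out a 2x2 factorial trial of 20,000 people followed for 5 years, with "independent and equal allocation of participants to each treatment in the trial (for Aim 1") and 80% compliance. It says that power was computed on the observed rate ratio.

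**Events and power.** Item a expects 1000 incident cases and continues: "Conservatively, we will validate 60% of these 1000 cases, or 600 cases, with 150 occurring in the placebo group", with fewer in the active groups if the agents work. The test is a log-rank test at level 0.05; whether it is one- or two-sided is not said for this aim. With one effective agent, "we will have 81% power to detect an observed RR of 0.70 (or 30% risk reduction") for the primary endpoint. Table 4 gives 0.81, 0.91 and 0.97 at observed RR 0.70, 0.65 and 0.60. On clustering, item a says that "some incident cases will occur within the same individuals, and these will be analyzed as discrete endpoints".

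**Synergy example.** If each agent alone reduces risk by 15% and the combination by a further 10%, "the RR comparing the combined group to the all placebo group would be 0.65". The text then says "Power for the total effects would increase to 91" per cent.

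**Compliance.** The Table 4 footnote reads "Observed RR=intent-to-treat RR assuming compliance 80%. True RR= with perfect compliance". The printed True RR values are 0.67, 0.61 and 0.56.

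**The concern.** A main effect in this design compares everyone assigned to an agent with everyone not assigned to it. Of 600 cases, about 300 would then fall in the control margin. The figure of 150 is 600/4, the double-placebo cell alone. If the powers rest on 150, then the power and detectable effect printed for the primary endpoint belong to a comparison of 5,000 with 5,000, which is not the one the plan makes primary. A reader who uses Table 4 to interpret a null result would take the trial to be less sensitive than the main-effect analysis is.

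The True RR column is a separate matter. It is meant to show what each observed RR implies under perfect compliance, and the gap between the two columns looks too small for 80% compliance.

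**Working it through.** **Inputs.** From the plan: 600 validated cases, 150 per cell if there is no effect, 5,000 per cell, 10,000 per margin, alpha 0.05, one effective agent, and 80% compliance already contained in the observed RR. Assumed: a two-sided test, no loss to follow-up, and independent cases.

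**Formulas.** With C control cases and 1:1 allocation, total events are E = C(1 + RR).

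- Schoenfeld: power = Φ(|ln RR| × √E / 2 − 1.96)
- Freedman: power = Φ(√E × (1 − RR)/(1 + RR) − 1.96)

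**Step 1: reproduce the printed figures.** At RR 0.70 with C = 150, E = 150 × 1.70 = 255, and Schoenfeld gives Φ(0.3567 × 15.97/2 − 1.96) = Φ(0.89) = 0.813. All rows, with Freedman in brackets:

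| Observed RR | Printed | Cell, C = 150: E | Cell power | Main effect, C = 300: E | Main-effect power |
|---|---|---|---|---|---|
| 0.70 | 0.81 | 255 | 0.813 (0.805) | 510 | 0.981 (0.979) |
| 0.65 | 0.91 | 247.5 | 0.923 (0.916) | 495 | 0.998 (0.997) |
| 0.60 | 0.97 | 240 | 0.977 (0.972) | 480 | 0.9999 (0.9998) |

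The cell basis fits every row to within about one point; the main effect fits none. Back-solving the printed powers for C gives 149, 142 and 141 by Schoenfeld, or 152, 147 and 148 by Freedman. A one-sided test does not rescue the main effect (0.99 at RR 0.70) and spoils the cell fit there (0.88 to 0.89).

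**Step 2: detectable effect at 80% power.** Solving for RR gives about 0.785 for the main effect (Freedman 0.784) and 0.704 for the cell contrast (0.702).

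**Step 3: clustering.** The documents do not say how many events share a person. If 10%, 20% or 30% of the information were lost (an assumed range), main-effect power at RR 0.70 would be 0.969, 0.950 or 0.921, and the detectable RR 0.774, 0.761 or 0.746. Main-effect power falls to 0.81 only when events halve, from 510 to 255.

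**Step 4: synergy example.** Expected cases by cell are 150, 150 × 0.85 = 127.5 twice, and 150 × 0.65 = 97.5.

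- Combined against all-placebo: RR 0.65, E = 247.5, power 0.923 (0.916). The stated 91% is about right for this contrast, and it equals Table 4's entry at RR 0.65.
- Main effect of either agent: RR = (127.5 + 97.5)/(150 + 127.5) = 225/277.5 = 0.811, E = 502.5, power 0.652 (0.649).

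**Step 5: True RR.** For compliance c, linear dilution gives True RR = 1 − (1 − observed)/c, and log-scale dilution gives observed^(1/c).

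| Observed RR | Printed True RR | Linear, c = 0.8 | Log scale, c = 0.8 | Linear, c = 0.9 |
|---|---|---|---|---|
| 0.70 | 0.67 | 0.625 | 0.640 | 0.667 |
| 0.65 | 0.61 | 0.5625 | 0.584 | 0.611 |
| 0.60 | 0.56 | 0.50 | 0.528 | 0.556 |

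The printed column equals linear dilution at 90% after rounding. Allowing for rounding, a single compliance that fits all three rows must lie between 0.899 and 0.909 (linear) or 0.874 and 0.886 (log scale). Neither range contains 0.80. Compliance of 80% with non-compliers keeping half the effect gives the same result (0.8 + 0.2 × 0.5 = 0.9), but no such rule is stated.

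**The case against.** The strongest reply is that item a discloses its input. It states the 150, and with four arms this is visibly one cell, so Table 4 is correct for what it was given. A cell contrast is also not foreign to the plan, because the analysis section mentions a comparison across treatment groups. The caption of Table 4 is not visible in the copy reviewed and may name the comparison. Part of this stands: the basis is inferred from the 150 and a close fit, and the fault is a mismatched basis rather than a slip in calculation. It does not settle the matter, because the running text attaches the 81% to the primary endpoint whatever the caption says. Item a also says that power would fall slightly if both agents worked independently, because there would be fewer events overall. That describes a main-effect analysis: in a contrast of one agent alone with double placebo, neither group receives the other agent and no events are lost. Nor is the choice presented as deliberate caution; the word for caution in item a governs the 60% validation rate.

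On True RR, the plan gives no dilution formula and does not say whether 80% is an average or an end-of-trial figure; compliance procedures are left to the parent protocol. That is a fair limit. What can be said is that neither simple dilution formula at 80% produces the column, so stating the formula used would be an adequate remedy.

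It is also fair that the 91% synergy figure is not an error, and that the recomputed powers depend on independent cases and a two-sided test.

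**Conclusion.** The concern holds, as a minor point. The power printed for total autoimmune disease is that of a 5,000 against 5,000 comparison. For the main effects named as primary, power at observed RR 0.70 is about 0.98, or 0.92 to 0.97 if 10% to 30% of events are lost to clustering. The mismatch understates power and calls for no change of design. These figures take 600 as the total when neither agent works, as item a's 150 per cell implies.

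The True RR column does not follow from the stated 80% compliance. Under simple dilution at that level, the perfect-compliance reductions are 37.5%, 44% and 50% (linear) or 36%, 42% and 47% (log scale), against the printed 33%, 39% and 44%. Confidence is high on the power figures. On True RR it is high that the column does not match simple dilution at 80%, but the size of any correction depends on the formula intended.

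**What to change.** 1. In Table 4 and item a, restate power for total autoimmune disease for the main effects: about 0.98, 0.998 and above 0.999 at RR 0.70, 0.65 and 0.60, with a detectable RR of about 0.785 at 80% power. State that the test is two-sided, if it is, and that cases clustered within persons are treated as independent. Label any cell-to-cell figures that are kept.
2. Correct the True RR column to 80% compliance, or state the compliance and formula that produced it.
3. Optionally, add beside the 91% synergy figure that main-effect power for either agent in that scenario is about 65%.
4. While recomputing Table 4, check which comparison the autoimmune thyroid disease column uses. No error is claimed there.

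The cost is text and table edits only. Sample size, endpoint and analysis are unchanged.
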